# 114 Chapter 2: Study Enrollment and Screening

# 115 **2.1 Participant Recruitment and Enrollment**

- Enrollment will proceed with the goal of having 30 completing the study pump use period. A maximum of 45 individuals may be enrolled into screening for the study in order to achieve this goal.
- 118 Study participants will be recruited at ~3 clinical centers in the United States without regard to gender, race,
- or ethnicity. There is no restriction on the number of participants to be enrolled by each clinical center toward the overall recruitment goal.
- 121 The study team will make every effort to have the following minimum numbers of participants complete 122 the trial in the specified subgroups at the time of enrollment:
- At least 50% of the participants with most recent available HbA1c  $\ge$  7.5%
- 124

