# 2.1.1 Informed Consent and Authorization Procedures

125 Potential eligibility may be assessed as part of a routine-care examination. Before completing any

- 126 procedures or collecting any data that are not part of usual care, written informed consent will be 127 obtained.
- 128 A parent/legal guardian (referred to subsequently as "parent") will be provided with the Informed Consent
- Form to read and will be given the opportunity to ask questions either via phone/videoconference or by
- 130 mail or email. If the parent is interested in the study, the investigator will schedule a virtual or in-person
- 131 visit to discuss study, and if the parent agrees to participation, the Informed Consent Form will be
- electronically signed through the JCHR website. A copy of the electronically signed consent form can be
- 133 printed by the parent and another copy will be printed by the site to add to the participant's study record.
- 134 This process is referred to as eConsent.
- 135 As part of the eConsent process, each parent will be asked to electronically sign an authorization for
- release of the participant's personal information (i.e., HIPAA Authorization). The investigator, or his or
- 137 her designee, will review the study-specific information that will be collected and to whom that
- information will be disclosed. After speaking with the parent, questions will be answered about the details
- regarding authorization.
- A participant is considered enrolled when the eConsent has been signed by the parent and theinvestigator.
- 142 The participants are not being asked to provide assent as (1) they will be less than 7 years of age, (2) it is
- 143 not expected that they would have the capacity to understand, and (3) their wear of the devices will be
- similar to the wear of these devices outside of the study.

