# 201 **2.4.1 Data Collection and Testing**

A history will be elicited from the parent and extracted from available medical records with respect to the participant's diabetes history, current diabetes management, other past and current medical problems, past and current medications, and drug allergies.

- 205 The following procedures will be performed at the screening visit:
- Informed consent process
- Assessment of eligibility
- Contact information (retained at the clinical center and not entered into study database)
- Demographics (date of birth, sex, race and ethnicity)
- Measurement of height/weight
- 211oIf the visit is conducted virtually, a verbal report of the participant's weight and verbal212report of height will be acceptable. A scale will be mailed to participants who do not213already have access to one.
- Determination of most recent HbA1c level from medical records or verbal report
- 215 Screening procedures will last approximately 1-2 hours.

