# **3.2 Study Pump Procedures and Training**

234 The study pump, study CGM, study blood glucose and ketone meters and associated supplies will be

provided to participants within 3 days of completion of the Screening visit once eligibility to continue in

the study has been confirmed. Dispensation of supplies may occur either in-person at the clinic, or via

237 delivery by other means (personal delivery, overnight shipment, etc.).

Training on use of the study pump will be completed within 10 days of completion of the Screening visit,

and closed-loop system use will begin at that time. Pump training may be delivered in one or more

sessions (in-person or virtual), as needed. During the training window, participants will be permitted to

use the study CGM and to use the study pump in open-loop mode if desired by the investigator.

Parents of participants will receive study pump training by a qualified trainer and will be fully instructed on the study insulin pump. The trainer will discuss topics such as: infusion site initiation,

cartridge/priming procedures, setting up the pump, charging the pump, navigation through menus, bolus

procedures including stopping a bolus, etc. The participating child will participate in training sessions to

the degree judged appropriate by the parent and trainer.

247

| 248
249
250        | Parents will be instructed to change the study insulin pump infusion set at least once every 3 days or per manufacturer guidelines, whichever is shorter.  |
|--------------------------|--|
| 251                      | Parents will be trained to use the bolus calculator following the standard t:slim X2 training.   |
| 252
253               | • The study team will assist the parent in study pump infusion site initiation and will start the participant on the study pump.   |
| 254
255               | • The parent will be supervised with the study pump during at least one meal or snack bolus to ensure participant understanding of the pump features.  |
| 256
257               | • The parent will be encouraged to review the literature provided with the pump and infusion sets after the training is completed.   |
| 258
259               | • The parent will be trained on severe hypoglycemia emergency procedures including removal of the study pump and administration of glucagon.   |
| 260                      | Pump training specific to the Control-IQ Technology functions will include:  |

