# 8.4.1 Safety Endpoints

- Severe Hypoglycemia (SH) events and SH event rate per 100 person-years
- Diabetic ketoacidosis (DKA) events and DKA event rate per 100 person-years
- Reportable hyperglycemia adverse events with or without ketosis
  - Events related to the study device
    - Events not related to the study device
- Reportable hypoglycemia adverse events that are not severe
- Number of calendar days with any ketone level  $\geq 1.0 \text{ mmol/L}$
- 871 *Hierarchical Safety Endpoints*
- CGM-Measured
  - % Time >250 mg/dL (non-inferiority)

| 874 | 
 
% Time <54 mg/dL (non-inferiority)
 
                                  |  |  |
|-----|--|--|--|
| 875 | Additional Safety Endpoints  |  |  |
| 876 | Other serious adverse events   |  |  |
| 877 | • Any adverse event rate per 100 person-years  |  |  |
| 878 | • Adverse device effects (ADE)   |  |  |
| 879 | • Serious adverse device events (SADE)   |  |  |
| 880 | • Unanticipated adverse device effects (UADE)  |  |  |
| 881 | 8.4.2 Efficacy Endpoints   |  |  |
| 882 | Hierarchical Efficacy Endpoints (tested for superiority compared with baseline)            |  |  |
| 883 | • CGM-Measured   |  |  |
| 884 | 
 
% Time in range 70–180 mg/dL
 
   |  |  |
| 885 | • Mean glucose   |  |  |
| 886 | • % Time >250 mg/dL  |  |  |
| 887 | • % Time <70 mg/dL   |  |  |
| 888 | $\circ$ % Time <54 mg/dL   |  |  |
| 889 | Secondary Endpoints  |  |  |
| 890 | • CGM-Measured   |  |  |
| 891 | 
 
% Time in range 70–140 mg/dL
 
   |  |  |
| 892 | • % Time >180 mg/dL  |  |  |
| 893 | • % Time >300 mg/dL  |  |  |
| 894 | $\circ$ % Time <60 mg/dL   |  |  |
| 895 | 
 
Glucose standard deviation
 
   |  |  |
| 896 | 
 
Glucose coefficient of variation
 
                                       |  |  |
| 897 | 
 
High blood glucose index (HBGI)
 
  |  |  |
| 898 | 
 
Low blood glucose index (LBGI)
 
   |  |  |
| 899 | • Weekly hyperglycemic event rate  |  |  |
| 900 | 
 
Weekly hypoglycemic event rate
 
   |  |  |
| 901 | o Binary   |  |  |
| 902 | 
 
% Time in range 70–180 mg/dL improvement from baseline to 8 weeks ≥5%
 
  |  |  |
| 903 | 
 
% Time in range 70–180 mg/dL improvement from baseline to 8 weeks ≥10%
 
 |  |  |
| 904 | 
 
% Time in range 70–180 mg/dL >70% and % time <70 mg/dL <4%
 
    |  |  |
| 905 | • Insulin  |  |  |

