#### 908 Exploratory Endpoints

| 909               | • Insulin   |  |  |
|-------------------|---|--|--|
| 910               | 0   | Total daily basal insulin (units/kg)   |  |
| 911               | 0   | Total daily bolus insulin (units/kg)   |  |
| 912               | 0   | Total daily manual bolus (units/kg)  |  |
| 913               | 0   | Total daily automated bolus (units/kg)   |  |
| 914               | 0   | Number of manual insulin doses per day   |  |
| 915               | 0   | Number of manual insulin doses with carb announcement per day                            |  |
| 916               | 0   | Average daily profile basal rate divided by total daily insulin in percentage points     |  |
| 917               | 0   | Average carbohydrate ratio daily profile (C:I) multiplied by total daily insulin         |  |
| 918               | 0   | Average insulin sensitivity factor daily profile (G:I) multiplied by total daily insulin |  |
| 919               |   | 8.5 Analysis Datasets and Sensitivity Analyses   |  |
| 920
921
922 | To be included in included in analyses of CGM and insulin outcomes, participants must provide at least 168 hours of CGM data for each of the baseline and trial phase and spend at least 50% of the study period in closed-loop mode. |  |  |

923 All participants who enroll in the PEDAP-AI study will be included in the safety analyses of endpoints

that are not measured by CGM. Analyses will include all events that occur between enrollment and the 3-924

Day Post-Study Safety contact or the end of the 71st day after the date of the Closed Loop Initiation 925

visit—whichever is earlier. For participants who do not complete the study, the date of the final contact 926 927

will be used in place of the 3-Day Post-Study Safety contact date.

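### Severe hypoglycemia, DKA and any-adverse-event rates count events from consent to the post-study contact over undefined person-time, and no rate for the device period is planned

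*Protocol*

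**What the plan says.** Protocol 8.5 and SAP 5.3 use the same words. The non-CGM safety population is everyone enrolled: "All participants who enroll in the PEDAP-AI study will be included in the safety analyses of endpoints" not measured by CGM. The event window is also given: "Analyses will include all events that occur between enrollment and the" 3-Day Post-Study Safety contact, or the end of day 71 after closed-loop initiation if that is earlier. For children who do not complete, the final contact date replaces the post-study contact.

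Enrollment precedes both eligibility and the pump. Protocol 2.1.1 states: "A participant is considered enrolled when the eConsent has been signed by the parent" and the investigator. Protocol 2.1 aims for 30 children completing the pump period and allows that up to "45 individuals may be enrolled into screening for the study in order to achieve this goal".

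Three safety endpoints in Protocol 8.4.1 and SAP 5.1 are rates. The first is "Severe Hypoglycemia (SH) events and SH event rate per 100 person-years"; DKA and any adverse event are given on the same scale. Neither document says what person-time goes into the denominator. Protocol 8.13 and SAP 7 plan tables of the listed endpoints and a listing of reportable events. Neither plans a rate limited to the time on the study system.

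**The concern.** The Protocol Summary gives the objective as safety data with initiation and use of the closed-loop system under AI-driven settings. Protocol 8.2 makes hypoglycemia and hyperglycemia adverse events part of the primary outcome. The planned event window is wider than that question. It includes days on the child's previous therapy, children who never receive the system, and the days after the switch to post-study therapy at the 8-week visit (Protocol 3.3.2 and 3.3.3). The CGM part of the same primary outcome starts at study pump use (Protocol 8.6, SAP 5.4), as do the system-use metrics (SAP 8).

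A reader who wants the event rate on the system would have to sort events from the listing and rebuild device person-time from the system-use tables. Relatedness coding does not do this sorting. It concerns cause rather than exposure time, and Protocol 6.2.3 and 6.2.4 say that severe hypoglycemia or DKA during device use will generally be called unrelated if the device worked as intended.

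**Working it through.** The documents state no rate or person-time total, so there is no figure to reproduce. The check asks how far a rate over the whole event window could differ from a rate over device time.

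**Inputs from the documents**
- 30 completers, up to 45 enrolled (Protocol 2.1).
- 8 weeks = 56 days on the system (Protocol Summary).
- Post-study contact 3 days after the final visit (Protocol 3.3.3).
- Pre-pump time: "Screening procedures will last approximately 1-2 hours" (Protocol 2.4.1); supplies are "provided to participants within 3 days of completion of the Screening visit"; and "Training on use of the study pump will be completed within 10 days of completion of the Screening visit" (Protocol 3.2).
- The day-71 cap does not bind for in-window visits: the latest contact is day 56 + 4 + 3 + 1 = 64.

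**Assumptions**
- Person-time follows the event window.
- Pre-pump time is 0 to 10 days. The documents give no expected pre-pump time and no expected number of screen failures.

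**Device time.** 30 × 56 = 1680 days; 1680/365.25 = 4.600 person-years. One event is 100/4.600 = 21.7 per 100 person-years.

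**Whole window.** Total days = 30 × (pre-pump + 56 + 3). Device share = 1680/total.

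| Pre-pump days | Total days | Person-years | Device share | One on-device event, per 100 person-years |
|---|---|---|---|---|
| 0 | 30 × 59 = 1770 | 4.846 | 94.9% | 20.6 |
| 3 | 30 × 62 = 1860 | 5.092 | 90.3% | 19.6 |
| 10 | 30 × 69 = 2070 | 5.667 | 81.2% | 17.6 |

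**Direction.** Let r be the off-device rate divided by the on-device rate. Then pooled rate / on-device rate = share + (1 − share) × r. At 0, 3 and 10 pre-pump days:
- r = 0 gives 0.949, 0.903, 0.812.
- r = 1 gives 1.000 throughout.
- r = 2 gives 1.051, 1.097, 1.188.

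**The other reading.** If the denominator is device time only while events count over the whole window, then with r = 1 the rate is inflated by total/1680: 1770/1680 = 1.054, 1860/1680 = 1.107, 2070/1680 = 1.232.

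**Imprecision.** The exact Poisson 95% limits for one event are 0.0253 and 5.572. Divided by 4.600 person-years and multiplied by 100, they give 0.6 to 121.1 per 100 person-years.

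**Non-completers, all with 10 pre-pump days for the completers**
- 15 screen failures at one day each: 1680/(2070 + 15) = 80.6%.
- 15 never-starters at 10 days each: 1680/(2070 + 150) = 75.7%.
- 15 who start after 10 pre-pump days and leave at day 14: (1680 + 210)/(1890 + 90 + 450) = 1890/2430 = 77.8%.
- The same 15 leaving at day 28: 2100/2640 = 79.5%.

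**The case against.** Counting from consent is deliberate and consistent: Protocol 6.2.1 defines an adverse event relative to enrollment and treats enrollment as consent. That stands. The all-enrolled view is a legitimate complete account of safety and should remain. CGM and system-use metrics naturally start at pump use, so the contrast with them does not show an error in event collection.

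The plan also has safeguards. Each DKA or severe hypoglycemia event is reviewed by the Medical Monitor and the DSMB for cause and attribution (Protocol 6.6.1). Possibly related events count as related (6.2.5). Hyperglycemia events are split by device relation, device effects are tabulated (8.4.1), and every reportable event is listed (8.13). With about 30 children, placing a rare event on or off the device is easy. This reduces the harm, but none of it supplies an on-device rate.

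The size is also open to challenge. Post-study days alone cost only 5% of the time, so pre-pump days are the main driver. Protocol 3.2 lets children use the study pump in open-loop mode during the training window; if that counts as device time, the share moves back from 81% towards 95%.

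A reader might infer that the plan puts off-device time in the denominator. The documents do not say so; they define the population and the event window only. A reader might also infer that the planned rates understate on-device risk. That does not follow either, because the direction depends on the unknown off-device rate.

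**Conclusion.** The point holds as a minor one. The three rates count events over a window wider than device use, their person-time is undefined, and no matched device-period rate is planned. Under either reading of the denominator, the planned figure is not the event rate on the study system.

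If person-time follows the event window, device time is about 95% to 81% of the total and one on-device event reads 20.6 to 17.6 instead of 21.7 per 100 person-years. This rests on 30 completers with 56 device days, 3 post-study days and 0 to 10 pre-pump days. Non-completers could lower the share to about 76% to 80% under the further assumptions shown.

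It would be tempting to say that about half of the person-time is off the device. That needs every limit at once: 38 pre-pump days for all completers (28 + 10, Table 1 footnotes) and 15 screen failures at 28 days each, giving 1680/(30 × 97 + 15 × 28) = 1680/3330 = 50.5%. Nothing in the documents suggests this is expected, and the severity does not rest on it.

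The shift is small beside the interval of 0.6 to 121.1 for one event. These rates are only tabulated, and no hypothesis test or formal stopping rule depends on them.

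**What to change.** Keep the all-enrolled adverse event counts and listing unchanged. Add to Protocol 8.5 and SAP 5.3 a device-exposed set: children who start the study pump. For this set, report the severe hypoglycemia, DKA and any-adverse-event rates per 100 person-years. Count both events and person-time from the start of study pump use to the 8-week visit, or to last device use if earlier. The starting point matches the one already used for CGM and system-use metrics.

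The cost is wording in two documents and one extra descriptive table. The added rates rest on slightly less exposure, 4.60 person-years against 4.85 to 5.67 in the cases tabulated, so they are slightly less precise. They may be higher or lower than the all-enrolled rates.

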#### 928 **8.6 CGM Metrics Calculations**

929 Baseline values for each CGM metric will be computed from the most recent 28 days of CGM data before 930 the Screening visit.

During the 8-week treatment period, CGM metrics will be calculated from the beginning of study pump 931 use until the end of the day before the final visit. 932

933

## 8.7 Insulin Metrics Calculations

934 Insulin metrics for comparisons between baseline and follow-up describe the seven days prior to the 935 visits.

936 Baseline insulin metrics will use data reported from the Diabetes Screening CRF. Insulin metrics at 8

weeks will be calculated using Tandem pump data. Insulin pump data on at least 5 of 7 days will be 937

required to calculate insulin metrics. Weight will only be recorded at the screening visit. All calculations 938

of units/kg will use this weight. 939

#### 8.8 Analysis of the Hierarchical Endpoints 940

Summary statistics will be reported for the hierarchical endpoints at baseline and during follow-up as well 941

as for differences from baseline. 24-hr profile plots will be drawn for follow-up. Boxplots will be drawn 942

for baseline and follow-up. Scatter plots will be drawn for follow-up versus baseline. 95% confidence 943

- intervals will be constructed for the change from baseline to 8 weeks. For % < 54 mg/dL and % > 250944
- mg/dL, tests of non-inferiority will be conducted using paired *t*-tests. The limits will be 0.5% for % < 54945

- 946 mg/dL and 3% for % >250 mg/dL. If these outcomes are determined to be non-inferior, they will be
- tested for superiority in a hierarchy with % 70-180 mg/dL, mean glucose, and % <70 mg/dL. Tests of 947
- superiority will be two-sided paired *t*-tests. If the distribution of changes is skewed, then robust methods 948 949 will be used instead.
- 950 To preserve the overall type 1 error among the formal comparisons, a hierarchy will be used in the following order: 951
- CGM % > 250 mg/dL (non-inferiority; limit = 3%) 952
- CGM % <54 mg/dL (non-inferiority; limit = 0.5%) 953 •
- 954 • CGM % 70–180 mg/dL (superiority)
- 955 Mean glucose (superiority) •
- CGM % >250 mg/dL (superiority) 956
- CGM % <70 mg/dL (superiority) 957 •
- CGM % <54 mg/dL (superiority) 958 •

If any of these comparisons result in a p-value >0.05, then formal testing will stop and p-values will not 959 960 be generated for any subsequent tests on the list. Note that the point estimates and confidence intervals will be generated for metrics regardless of statistical significance. 961

962

## **8.9** Analysis of Secondary Endpoints

Summary statistics will be reported for baseline, follow-up, and difference from baseline. For all 963

continuous outcomes, boxplots will be drawn for baseline and follow-up and scatter plots will be drawn 964 965 for follow-up versus baseline. 24-hr profile plots will be drawn for continuous CGM-measured endpoints during follow-up. 966

Change over time will be compared with a paired *t*-test when the change appears approximately normal, 967 and using robust methods when the change is skewed. Ninety-five percent confidence intervals of the 968 changes from baseline will be derived from these tests. 969

970 For the binary outcome % time in range 70–180 mg/dL >70% and % time <70 mg/dL <4%, the

proportion will be compared between baseline and follow-up with Barnard's exact test. A ninety-five 971

- percent confidence interval of the change from baseline will be derived from this test. 972
- 973

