# **PROTOCOL SUMMARY**

| PARTICIPANT AREA       | DESCRIPTION   |  |
|------------------------|---|--|
| Title                  | The Pediatric Artificial Pancreas Automated Initialization trial (PEDAP-AI): A Pilot
Study of AI Advisor-Driven Pump Initiation and Parameter Adaptation in Young Children
with Type 1 Diabetes   |  |
| Précis                 | A single-arm pilot study of AI Advisor-driven at-home closed loop system initiation and parameter adaptation in youth age 2 to <6 years old.  |  |
| Investigational Device | Tandem t:slim X2 with Control-IQ and t:connect mobile application and Dexcom G6 or G7 system, connected to UVA cloud-based Physician Dashboard  |  |
| Objectives             | The objective of the study is to obtain safety data and exploratory glycemic control data with initiation and use of a closed loop control (CLC) system (t:slim X2 with Control-IQ Technology) in young children with initial selection of pump parameters and subsequent periodic parameter adjustment driven by an AI-based Advisor system over a 8-week period.  |  |
| Study Design           | In this single-arm intervention trial, all participants will use the study system (pump and CGM) in closed-loop mode for 8 weeks.   |  |
| Number of Sites        | ~3 US clinical centers  |  |
| Endpoints              | SafetyThe key safety outcomes are adverse events related to hypoglycemia and hyperglycemia,
CGM-measured time spent below 54mg/dL, and CGM-measured time spent above
250mg/dL. CGM-measured endpoints will be tested against baseline for non-inferiority.EfficacyGlycemic outcomes including time in target range 70-180 mg/dL (TIR) and various other
CGM measures of hypo- and hyperglycemia will be assessed and tested for superiority
against baseline and a matched historical control population from the prior PEDAP study
that did not involve the use of any AI-driven pump parameters.   |  |

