#### 853 Percentage above 250 mg/dL:

- a. *Null Hypothesis*: The difference in mean CGM-measured % above 250 mg/dL between the 8 weeks follow-up and baseline is greater than or equal to +3% (non-inferiority).
  b. *Alternative Hypothesis*: The difference in mean CGM-measured % above 250 mg/dL between the
- 857 8 weeks follow-up and baseline is less than +3%.
- 858 **8.3 Sample Size**

The study has not been formally powered to test any a priori hypothesis. The goal is to have at least 30 participants complete the 8-week trial period. Some outcomes will be compared between these participants and a sample of participants from the prior PEDAP study.

- 862 **8.4 Endpoints**
- 863

867

868

873

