Summary statistics will be reported for the hierarchical endpoints at baseline and during follow-up as well 142 as for differences from baseline. 24-hr profile plots will be drawn for follow-up. Boxplots will be drawn 143 144 for baseline and follow-up. Scatter plots will be drawn for follow-up versus baseline. 95% confidence intervals will be constructed for the change from baseline to 8 weeks. For% <54 mg/dL and% >250 145

mg/dL, tests of non-inferiority will be conducted using paired *t-tests*. The limits will be 0.5% for \ll <54 146

147 mg/dL and 3% for%>250mg/dL. If these outcomes are determined to be non-inferior, they will be

- tested for superiority in a hierarchy with% 70-180 mg/dL, mean gluco, se and% <70 mg/dL. Tests of 148
- 149 superiority will be two-sided paired *t-tests*. If the distribution of changes is skewed then robust methods
- will be used instead. 1SO

- 151 To preserve the overall type 1 error among the formal comparisons, a hierarchy will be used in the
- 152 following order:
- CGM% >250 mg/dL (non-inferiority; limit=3%)
- CGM% < 54 mg/dL (non-inferiority; limit = 0.5%)
- CGM% 70-180mg/dL(superiority)
- Mean glucose (superiority)
- CGM% >250 mg/dL (superiority)
- CGM% <70 mg/dL (superiority)
- CGM% <54 mg/dL(superiority)

160 If any of these comparisons result in a p-value >0.05, then formal testing will stop and p-values will not

be generated for any subsequent testson the list. Note that the point estimates and confidence intervals
 will be generated for metrics regardless of statistical significance.

- 163 6.2 Analysis of SecondaryEndpoints
- 164 6.2.1 Comparison with Baseline

165 Summary statistics will be reported for baseline, follow-up, and difference from baseline. For all

166 continuous outcomes, boxplots will be drawn for baseline and follow-up and scatter plots will be drawn
 167 for follow-up versus baseline. 24-hr profile plots will be drawn for continuous CGM-measured endpoints
 168 during follow-up.

- 169 Change over time will be compared with a paired *t-test* when the change appears approximately normal,
- and using robust methods when the change is skewed. Ninety-five percent confidence intervals of the
- 171 changes from baseline will be derived from these tests.
- 172 For the binary outcome% time in range 70-180 mg/dL>70% and% time <70 mg/dL <4% the
- 173 proportion will be compared between baseline and follow-up with Barnard's exact test. A ninety-five

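### Barnard's exact test assumes two independent samples, but the plan applies it, and derives the 95% interval from it, to baseline and follow-up status in the same children

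*Protocol*

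**What the plan says.** Protocol 8.9 covers the secondary baseline-versus-follow-up comparisons. For the composite binary endpoint (time in 70–180 mg/dL above 70% and time below 70 mg/dL under 4%), the "proportion will be compared between baseline and follow-up with Barnard's exact test". The interval follows from it: a 95% "percent confidence interval of the change from baseline will be derived from this test". SAP 6.2.1 repeats both sentences ("proportion will be compared between baseline and follow-up with Barnard's exact" test).

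Three other statements settle what kind of data these are:

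- The design has no concurrent control. The Protocol Summary says: "In this single-arm intervention trial, all participants will use the study system (pump and CGM) in closed-loop mode for 8 weeks".
- Protocol 8.5 (and SAP 5.3) admits a child to the CGM analyses only with "168 hours of CGM data for each of the baseline and trial phase". Every analysed child therefore has a status at both times.
- For continuous endpoints the same section respects the pairing: "Change over time will be compared with a paired" t-test, or robust methods if the change is skewed.

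On size, Protocol 8.3 says: "The goal is to have at least 30" children completing, with no formal power calculation. Neither document names a paired test for binary data. The comparison with the earlier PEDAP cohort, which does involve independent groups, has its own logistic model (Protocol 8.10, SAP 6.2.2), so Barnard's test is not meant for that.

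**The concern.** Barnard's test compares two binomial proportions from separate groups of people. Fed with the baseline and follow-up counts, it treats about 30 children as 60 unrelated observations. It sees only how many met the target at each time and not which children moved in or out of target, which is where the evidence on change lies when the same children are measured twice.

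The variance is wrong for the same reason. For n pairs, with p1 and p2 the proportions on target at baseline and follow-up and p11 the proportion on target at both,

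Var(difference) = [p1(1−p1) + p2(1−p2) − 2(p11 − p1·p2)] / n.

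Barnard's test leaves out the last term. If a child on target at baseline is more likely than others to be on target later, that term is positive, the true variance is smaller than assumed, and the plan gives p-values that are generally too large and an interval that is too wide. If the correlation were negative, the error would run the other way.

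In a pilot without formal power, the estimate and its interval are the main result for this endpoint. The p-value also joins the false discovery rate category for baseline-versus-follow-up CGM endpoints (SAP 15), so it can influence which other endpoints in that category are declared significant.

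**Working it through.** **Inputs.** n = 30 pairs (Protocol 8.3). Two-sided 0.05 is assumed, to match the 95% interval, because no false discovery rate level is stated. The documents give no proportion on target and no within-child correlation (phi), so these are assumptions shown over a range. The plan gives no figure for this endpoint, so there is nothing to reproduce.

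**Step 1. Barnard's test cannot see who changed.** It uses the pooled score statistic on the two marginal counts, maximised over the common proportion. Exact McNemar uses only the children who changed: with g gaining and l losing the target, l ≤ g,

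p = 2 × Σ(k=0..l) C(g+l, k) / 2^(g+l).

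For example, g = 7 and l = 0 gives 2/128 = 0.016; g = 8 and l = 1 gives 2 × (1+9)/512 = 0.039. Holding the margins at 6/30 and 13/30:

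| Gained / lost | Barnard | Exact McNemar | Unconditional exact McNemar |
|---|---|---|---|
| 7 / 0 | 0.056 | 0.016 | 0.009 |
| 8 / 1 | 0.056 | 0.039 | 0.020 |
| 9 / 2 | 0.056 | 0.065 | 0.042 |
| 10 / 3 | 0.056 | 0.092 | 0.056 |

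Barnard's p-value is the same in all four rows although the evidence differs.

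**Step 2. Other tables of 30 children.** phi = (both × neither − gained × lost) / √(product of the four margins). For the first row, phi = (8×15 − 7×0)/√(8×22×15×15) = 120/199 = 0.60.

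| Both / gained / lost / neither | Change | phi | Barnard | Exact McNemar |
|---|---|---|---|---|
| 8 / 7 / 0 / 15 | 8/30 to 15/30 | 0.60 | 0.070 | 0.016 |
| 12 / 6 / 0 / 12 | 12/30 to 18/30 | 0.67 | 0.155 | 0.031 |
| 10 / 8 / 1 / 11 | 11/30 to 18/30 | 0.48 | 0.086 | 0.039 |
| 6 / 9 / 2 / 13 | 8/30 to 15/30 | 0.30 | 0.070 | 0.065 |
| 5 / 10 / 3 / 12 | 8/30 to 15/30 | 0.15 | 0.070 | 0.092 |

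**Step 3. True type I error at nominal 0.05.** All paired outcomes for n = 30 were enumerated exactly, with the same proportion on target at both times (20%, 30% or 50%) and p11 = p1·p2 + phi·√(p1(1−p1)p2(1−p2)). The range is over the three proportions.

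| phi | Barnard | Exact McNemar | Unconditional exact McNemar |
|---|---|---|---|
| −0.2 | 0.062–0.069 | 0.024–0.030 | 0.043–0.047 |
| 0 | 0.042–0.047 | 0.022–0.028 | 0.043–0.047 |
| 0.3 | 0.016–0.018 | 0.015–0.023 | 0.043–0.047 |
| 0.5 | 0.005–0.006 | 0.008–0.018 | 0.045–0.048 |
| 0.7 | 0.0005–0.0008 | 0.002–0.007 | 0.029–0.047 |

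**Step 4. Power, same enumeration.**

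| True change | phi | Barnard | Exact McNemar | Unconditional exact McNemar |
|---|---|---|---|---|
| 20% to 40% | 0 | 0.37 | 0.28 | 0.37 |
| 20% to 40% | 0.3 | 0.34 | 0.38 | 0.49 |
| 20% to 40% | 0.5 | 0.31 | 0.49 | 0.67 |
| 20% to 45% | 0.3 | 0.53 | 0.57 | 0.67 |
| 20% to 45% | 0.5 | 0.53 | 0.74 | 0.88 |

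Two further scenarios, specified by cell, agree. With 20% on target at both times, 22% gaining and 2% losing, power is 30% for Barnard against 49% for exact McNemar. With 25%, 25% and 3%, it is 36% against 54%.

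**Step 5. Interval width.** Wald half-widths show the order of magnitude (the plan's interval would be obtained from Barnard's test, so it would differ somewhat). For 6/30 to 13/30 with 7 gained and 0 lost:

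- As independent: 1.96 × √(0.200×0.800/30 + 0.433×0.567/30) = 22.8 points.
- As paired: 1.96 × √(7 − 7²/30)/30 = 15.1 points.

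With 10 gained and 3 lost, the paired half-width is 22.0 points, close to the independent value.

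**The case against.** The case on the other side accepts that the data are paired and disputes how much it matters.

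- **The striking examples assume strong correlation.** The first three tables in Step 2 have phi of 0.48 to 0.67, and the documents give no value. Therapy changes between the periods, at least for children coming from injections, and the status is a double threshold, so low correlation cannot be excluded. This stands. At phi of about 0.3 exact McNemar gains little, and near 0 it does worse than Barnard.
- **Exact McNemar is itself conservative at n = 30.** This also stands, but it bears on which paired test to choose. The unconditional paired test holds its level near 0.05 for phi from −0.2 to 0.5. In the 20% to 40% case it matches Barnard's power at phi = 0 and exceeds it at 0.3 and 0.5.
- **The error would not manufacture a benefit.** With positive correlation it is conservative. Excess false positives (0.062–0.069) appear only at phi = −0.2. This stands.
- **The stakes are low.** This is one secondary endpoint, outside the hierarchy, and the two underlying CGM percentages are tested separately with paired methods. The point estimate of change is unaffected. One p-value among the ten continuous secondary CGM endpoints may shift the false discovery rate step, but no changed decision has been shown. This stands too, and it limits the severity.

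None of these points makes an independent-samples test valid for paired data.

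**Conclusion.** The point holds. Both documents prescribe an independent-samples test, and an interval derived from it, for two proportions measured in the same children, and nothing elsewhere in the plan corrects this.

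The size depends on the within-child correlation, which is an assumption. Near zero, Barnard's test is close to its nominal level and little is lost. At 0.5, its true level is about 0.005 instead of 0.05. Power for a rise from 20% to 40% is then 0.31, against 0.49 for exact McNemar and 0.67 for the unconditional paired test. An interval can be about half as wide again as it should be (22.8 against 15.1 points in the Step 5 example with no losses). The direction is conservative for any positive correlation.

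This should be corrected, but it does not threaten the trial's main conclusions: the safety non-inferiority tests and the superiority hierarchy are untouched.

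**What to change.** In Protocol 8.9 and SAP 6.2.1, replace Barnard's test for this endpoint with a test for paired proportions: either the exact McNemar test or an unconditional exact test for paired data. The unconditional test is preferable at about 30 pairs because it stays closer to the nominal level and has more power. Name one of them in advance. Take the 95% interval for the change from a paired-difference method such as Tango's score interval. Report the 2×2 table of baseline by follow-up status, so that gains and losses are visible.

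If a paired, unconditional analogue of Barnard's test was intended all along, the text should say so explicitly.

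The cost is one sentence in each document, with no new data and no effect on participants. The change should be made before the analysis, because switching tests once the results are known would look post hoc.
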